22 March 2021

Dear Sir/Madam,

Official Title: A Controlled trial of Yoga in Pediatric Inflammatory Bowel Disease

NCT No: NCT03338894

Date of document: 14 February 2021

I am writing to provide the updated study protocol of the above said study. The protocol document has been approved by the Institutional Review Board.

Thank you

[name]

Title of Project:

A Controlled trial of Yoga in Pediatric Inflammatory Bowel Disease

PI: [name]

Co-investigators: [name]; [name]; [name]; [name], DO; [name]; [name]; [name]; [name], APN; [name]; [name], DO; [name]; [name]

Lay Summary:

Approximately 25% of Inflammatory bowel disease (IBD) is diagnosed in the pediatric age group, with the peak age of onset in the adolescent years¹. IBD adds additional stressors of a chronic disease with unpredictable and potentially embarrassing symptoms to the expected challenges of psychological and social adjustment that teenagers face. Various techniques, such as psychotherapy programs and IBD overnight camp experiences, have been studied to decrease psychological distress and improve quality of life. Stress, and particularly how stressful events are perceived, may play a role in triggering IBD flares. Complementary and alternative medicine (CAM), especially mind-body techniques are used often by pediatric IBD patients and may be beneficial in decreasing stress and improving quality of life (QOL). Yoga may be well suited as an adjunct to conventional IBD therapy to decrease stress, provide a greater sense of bodily control and improve QOL.

The primary goal of this project is to determine if a structured Yoga program, in addition to standard medical therapy, improves HRQOL in pediatric patients diagnosed with inflammatory bowel disease (IBD). We will also examine if the yoga program improves self-efficacy, which is a person's belief about their ability to influence events that affect their lives. Disease response and remission rates will be followed as well, in order to stratify HRQOL outcomes in the yoga group.

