The study will prospectively enroll patients seen at the Pediatric IBD center of the Goryeb Children's Hospital. All pediatric patients diagnosed with IBD will be offered enrollment in the study. Data collection surveys will be initially completed at the time of consent (time 0), start of the yoga (time 1) session, end of the yoga session (time 2) and three months after completion (time 3) to determine if the effects of yoga are lasting. Each patient will serve as their own control with the difference between time of enrollment (time 0)/start of yoga (time 1) and start of yoga (time 1)/end of yoga (end of 2) being compared. Patients will enroll in a twelve class series offered twice a year. The classes will be open to a maximum of ten students and will continue to be offered once a week with encouragement to practice daily at home. Patients will have the option to attend a fall or spring set of classes to increase flexibility and improve enrollment.

Through the entire study period patients will receive standard medical therapy as determined by their specific pediatric gastroenterologist. Clearance by their primary gastroenterologist will be required in the 8 week time period prior to starting yoga to confirm they are healthy enough to start yoga.

Sample Size: Based on what has been determined to be the minimal clinically significant difference¹⁴ of HRQOL using the pedQL survey, we would need 34 patients in total as each patient will serve as their own control. . With a sample size of 34 patients, there will be 80% power to detect a 10-point increase (improvement) in average total PedsQL score (0-100 scale)]. The sample size calculation was based on standard deviation of the total score in the Control group = 15.4, probability of Type I error (alpha) of 0.05, and probability of Type II error (beta) of 0.20. That is, in only 20% of the times we will fail to reject the null hypothesis when it is in fact false; i.e. there is a difference.

Recruitment will be feasible over a two-year study time frame as we care for over 800 active IBD patients in our center.

Inclusion Criteria:

- Both male and female patients with IBD.
- Age 10-17 years
- Not currently practicing specific mind-body techniques (yoga, pranayama, biofeedback, hypnosis, guided imagery)
- Diagnosis of IBD

Exclusion Criteria: Other Chronic systemic disease ex. RA, CF, Celiac. Any chronic neurologic condition.

Yoga Introduction:

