The teacher will present modifications to the routine (such as avoiding inverted poses) for patients who are menstruating or having an active flare of GI symptoms.

Data collection measures :

- Impact III:

This is a validated, disease-specific pediatric questionnaire that measures HRQOL in pediatric IBD¹⁶ patients age 9-17 years. It consists of 35 questions and six domains: IBD symptoms, systemic symptoms, emotional functioning, social functioning, body image, and treatment/interventions. The answers are scored on a 5 point Likert response scale.

- Peds QL:

This is a validated pediatric questionnaire that measures general HRQOL in children ages 8-17 years¹⁴. It consists of 23 questions in areas of social, school, emotional and physical functioning. The answers are scored on a 5 point scale and then reverse scored and linearly transformed to a 0-100 scale.

- General Self-Efficacy Scale:

This is a widely used simple 10 item scale that measures a patient's a general sense of perceived self-efficacy, aiming to predict coping with daily life as well as adaptation after stressful life events¹⁷. It is a measure that has been validated in adolescents age 12 and above.

- PCDAI and PUCAI :

The Pediatric Crohn Disease Activity Index (PCDAI) and Pediatric Ulcerative Colitis Activity Index (PUCAI) are validated disease activity indices that include patient symptoms in the previous seven days, physical exam findings, growth parameters

and laboratory studies¹⁸. The information needed to complete this index will be available through the patient's chart as the data collected is part of routine care.

- Physician Global Assessment :

This is a global assessment is part of routine care and determined by the patient's primary GI doctor. The assessment is a global measure of disease activity with the following five categories: inactive, mild, moderate, severe, NA/unknown.

- Short Crohn Disease Activity Index (SCDAI):

This tool has been validated for use in adult crohn's disease patients but is particularly useful for measurement of short-term disease activity and wellbeing. This data will be collected in the crohn's disease patients and includes liquid stools, well-being and abdominal pain²⁵.

- Medication use data:

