We will record what medications the patient is currently using, including steroids, biologics and immune modulators. The dose of medications will also be recorded in order to determine such information as the total dose of steroids, per patient over the study period.

- Yoga Questionnaire:

The yoga questionnaire will consist of questions about past exercise experience, use of other non-mind/body CAM such as probiotics, herbs and supplements. Post yoga the questionnaire will consist of questions if they plan to continue to practice after the study is complete.

- Follow up questionnaire:

Questionnaire will be sent for those subjects who have completed at least nine classes. The follow up questionnaire consists of 5 questions to evaluate if they are still practicing yoga, any benefit from being in the yoga study, has it helped manage their IBD and would they participate in a follow up yoga study.

In addition to the questionnaire/outcome measure collected at baseline and at the different endpoints (Impact III, peds QL, self efficacy scale, PCDAI, PUCAI), baseline demographic and clinical data will be gathered for each patient in the study. Those include age, gender, race, disease type (crohn's, UC), date of diagnosis, areas of bowel involved, medications and dose of steroids.

V. Planned Data Analysis:

Baseline demographic data will be collected and descriptive statistics will be used to profile the patient population. Clinical factors collected at baseline and post intervention and the differences will be

analyzed between the yoga and control group. Categorical data will be analyzed using chi-square or Fisher's exact tests. The distribution of all continuous data will be examined. For continuous variables whose distributions approximate normality, a t-test will be used for comparisons. When normality assumptions are not satisfied, the non-parametric Mann-Whitney U test will be utilized.

The data from the questionnaires will be collected via REDCap secure access.

Statistical significance is considered at $p < 0.05$. All statistical analyses will be performed using MINITAB 17.

VI. Benefits and Risks:

We anticipate the participants who complete the yoga program will have improved HRQOL and self-efficacy. All participants may experience a personal satisfaction by their contribution to a clinical investigation.

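### If change in the Physician Global Assessment is tested, the plan's only categorical rule (chi-square or Fisher) ignores grade order and pairing, and NA/unknown has no stated handling (minor)

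*Combined protocol and SAP*

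**What the plan says.** Section IV, under the data collection measures, describes the PGA as part of routine care, assigned by the patient's own gastroenterologist. It is a "global measure of disease activity with the following five categories: inactive, mild, moderate, severe, NA/unknown".

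Section V does not name the PGA. Its rule for categorical variables is "Categorical data will be analyzed using chi-square or Fisher's exact tests". A rank test appears only as the fallback for continuous variables: "When normality assumptions are not satisfied, the non-parametric Mann-Whitney U test will be utilized". The comparison is introduced by "Clinical factors collected at baseline and post intervention and the differences will be" and is then described as one between yoga and control groups. The design has no separate control group; Section IV says "Each patient will serve as their own control".

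Two other places bear on how much weight the PGA carries. The end of Section IV refers to the "questionnaire/outcome measure collected at baseline and at the different endpoints (Impact III, peds QL, self efficacy scale, PCDAI, PUCAI"), and the PGA is not in that list. The Lay Summary says "Disease response and remission rates will be followed as well, in order to stratify HRQOL outcomes in the yoga group". The documents contain no rule for missing data.

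**The concern.** The four PGA grades have a natural order, and the question of interest is whether patients move along it. Chi-square and Fisher's exact test treat the grades as labels: a shift towards inactive disease counts no differently from any other rearrangement of the same size. They also treat two ratings of one patient as ratings of two different people. Both features cost power.

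The fifth category is a separate matter. NA/unknown is the absence of a rating, not a state of disease. Nothing in the plan sets it aside, so an analyst could tabulate all five categories. Excess NA at one visit would then add to the test statistic even if rated disease activity had not moved. At stake is any statement about disease activity that rests on the PGA, which is the only single activity instrument in the protocol used for both Crohn's disease and ulcerative colitis.

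**Working it through.** The plan states no power or effect figure for the PGA, so there is none to reproduce. The 34 below is the planned number of patients (Section IV, Sample Size), which was set for the PedsQL. Grade distributions, odds ratios, within-patient correlations and NA rates are assumptions.

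**1. Order.** Take 34 ratings at each visit, inactive to severe: 16, 10, 6, 2 and 8, 10, 10, 6. Column totals are 24, 20, 16, 8, so the expected counts in each row are 12, 10, 8, 4.

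Chi-square = 2 × (4²/12 + 0²/10 + 2²/8 + 2²/4) = 2 × (1.333 + 0 + 0.5 + 1) = 5.67 on 3 df, p = 0.129.

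This value is the same however the four columns are arranged. A rank test on the same counts gives p = 0.019 in the true order, and p = 0.92 and 0.54 in two scrambled orders. The rank test uses the order and chi-square does not.

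**2. Power.** Start from 40/35/20/5% and multiply the odds of being at or below each grade by a common odds ratio. For a ratio of 2, the cumulative proportions 0.40, 0.75, 0.95 have odds 0.667, 3, 19. Doubled, these are 1.333, 6, 38, or 0.571, 0.857, 0.974. The shifted distribution is 57.1/28.6/11.7/2.6%. Simulated power at two-sided 5%, 34 patients:

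| Ratings at the two visits | Test | OR 2 | OR 2.5 | OR 3 |
|---|---|---|---|---|
| Independent | Chi-square, 4 grades | 19% | 35% | 45% |
| Independent | Rank test (Mann-Whitney) | 31% | 50% | 64% |
| Correlation 0.5 | Chi-square, 4 grades | 15% | 28% | 43% |
| Correlation 0.5 | Signed-rank | 47% | 69% | 82% |

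The first pair isolates the loss from ignoring order. The second adds the loss from ignoring pairing, and is the relevant pair when each patient is their own control. The correlation is on the latent scale behind the grades. Repeat runs agree within about three percentage points. With a baseline of 30/35/25/10% and independent ratings, the order effect is similar: about 21/36/49% against 34/54/67%.

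**3. NA/unknown kept as a fifth level.** Suppose rated patients have exactly the same distribution at both visits, and k of 34 are NA at one visit only. The NA column contributes 2 × (k/2)²/(k/2) = k. The four rated columns together contribute 2 × (k/2)²/((68 − k)/2) = k²/(68 − k). So chi-square = k + k²/(68 − k) on 4 df, whatever the grade distribution.

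- k = 8: 8 + 64/60 = 9.07, p = 0.060.
- k = 9: 9 + 81/59 = 10.37, p = 0.035.

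With the NA column removed, the statistic is 0. In simulated trials chance differences among the rated patients add to this, so rejection can occur with fewer NA. With no true change in disease, the five-category chi-square rejects at nominal 5% as follows:

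| NA at one visit / the other | Rejection |
|---|---|
| 0% / 20% | about 47–61% |
| 5% / 20% | about 19–24% |
| 10% / 20% | about 6–11% |
| Equal | no more than 5% |

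The upper end of each range is for independent ratings and the lower end for strongly correlated ones (about 0.8). A signed-rank test with NA set to missing stays at about 4–5%.

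**The case against.** The strongest reply is that the PGA is not shown to be a tested outcome. The aims are quality of life and self-efficacy. The list of endpoint measures leaves the PGA out, and response and remission are to be used to stratify quality-of-life results. They could be taken from the PCDAI and PUCAI, which are on that list and between them cover both diseases. This stands, and it is why the point is conditional and minor.

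A reader might infer that the plan makes NA/unknown an outcome level, so that a disease-response result is likely to be significant through missing ratings alone. The documents do not support that. Section IV lists the response options of a rating, and Section V is silent on NA. That is a gap, not a rule.

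Nor do the documents show that NA will be unequal between visits. One might argue that NA is likelier at the class dates than at consent, because the PGA comes from routine care. But Section IV requires clearance by the primary gastroenterologist in the 8 weeks before yoga starts, and that same doctor assigns the PGA, so a rating near time 1 is plausible. If NA were similarly frequent at times 1 and 2, that comparison would not be inflated. The highest rejection rates need no NA at all at one visit and 20% at the other.

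It may also be said that correcting the unpaired tests would mend this sentence anyway. Only partly: McNemar-type tests on nominal categories would respect pairing and still ignore order, and NA would still need a rule.

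**Conclusion.** The point holds in a limited form. If PGA change is tested under the rule in Section V, the test discards both the order of the grades and the pairing. Under the stated assumptions that costs roughly 32 to 41 percentage points of power against signed-rank (47 − 15 = 32, 69 − 28 = 41, 82 − 43 = 39), of which order alone accounts for roughly 12 to 19 in the independent case (31 − 19 = 12, 50 − 35 = 15, 64 − 45 = 19). This part needs no assumption about NA.

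The NA part is an omission that could mislead only if two things happen: NA is tabulated as a level, and its frequency differs materially between the visits compared. Neither is stated, so no single false-positive rate can be attached to the plan. The PedsQL comparison, the aims and the sample size are not touched.

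**What to change.** Add to Section V that the PGA, if compared over time, is analysed on its four ordered grades with a within-patient ordinal method. This could be a signed-rank test on the change in grade, or an ordinal logistic mixed model with a patient effect. Name the visits compared. State that NA/unknown is treated as missing and that its count is reported at each time. Keep chi-square and Fisher's exact test for unordered variables measured on separate patients.

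This takes a sentence or two and no new data. The cost is that patients with an unknown PGA drop out of that one comparison (under signed-rank, anyone unrated at either visit), so the NA counts should sit beside the result.

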Patients will each serve as their own control and complete questionnaires at enrollment and at the start and end of the 12-week group yoga class sessions. They will also complete the questionnaires three months after finishing the class sessions. . The program will consist of a live group class session over 12 weeks. Baseline and follow-up questionnaires will be used to determine there are changes in QOL, self-efficacy, and disease response.

I. Specific Aims:

1. Primary Aim: To determine if a structured Yoga program, in addition to standard medical therapy, improves health related quality of life (HRQOL) in pediatric patients diagnosed with IBD

2. Secondary Aim:

To determine if, in pediatric patients recently diagnosed with IBD, a structured Yoga program:

- Improves self-efficacy

II. Background and Significance:

Approximately 25% of Inflammatory bowel disease (IBD) is diagnosed in the pediatric age group with the peak age of onset in the adolescent years¹. Adolescence is a time of great psychosocial growth. IBD adds additional stressors of a chronic disease with unpredictable and potentially embarrassing symptoms. Side effects of steroid treatment, such as acne, weight gain, and mood changes, as well as delayed puberty, may further ostracize youth with IBD. The incidence of psychiatric disorders, is increased compared to healthy children and is comparable to other chronic diseases such as cystic fibrosis². HRQOL may be impaired by issues of pain, school absences, and concerns about the chronic nature of IBD and patients with increased disease severity often have worse HRQOL².

Various strategies have been tried to improve HRQOL and psychosocial functioning in pediatric IBD patients. A prospective analysis of HRQOL and anxiety in children attending a one week camp sponsored by the Crohn's and Colitis foundation of America demonstrated improvement in the quality of life³. A cognitive behavioral therapy (CBT) program, which included relaxation training and pain-coping strategies, increased a feeling of control and decreased helplessness in adolescents⁴. More recently a skills based psychological intervention program, which included relaxation, imagery and deep-breathing as part overall CBT program, showed significant reductions in somatization symptoms in a group of adolescent girls with IBD and their parents when pre and post-treatment variables were compared⁵.

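### The analysis section compares a yoga group with a control group that this one-cohort design does not have, and names independent-sample tests but no paired one

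*Combined protocol and SAP*

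**What the plan says.** The Lay Summary describes a single cohort: "Patients will each serve as their own control and complete questionnaires at enrollment", with further questionnaires at the start and end of the classes and three months later. Section IV (Participants and Enrollment) repeats this: "Each patient will serve as their own control with the difference between time of enrollment (time 0)/start of yoga (time 1"; the sentence goes on to set that difference against the one from start to end of yoga. Below, T0 is enrolment, T1 the start and T2 the end of yoga. The Sample Size paragraph relies on the same idea: "we would need 34 patients in total as each patient will serve as their own control". No control arm or allocation is described.

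Section V (Planned Data Analysis) is the only analysis section. It says that clinical factors are collected at baseline and after the intervention and that the differences are "analyzed between the yoga and control group". The tests follow directly: "Categorical data will be analyzed using chi-square or Fisher's exact tests"; for roughly normal continuous variables, "a t-test will be used for comparisons"; otherwise, "When normality assumptions are not satisfied, the non-parametric Mann-Whitney U test will be utilized". No paired t-test, signed-rank test, McNemar test, repeated-measures model or mixed model appears anywhere in the document.

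**The concern.** Sections IV and V describe different studies. Taken literally, Section V cannot be carried out, because there is no second group. If the control group is read as the T0–T1 control period, the two sets of changes come from the same patients and share the T1 score, so they are generally correlated. Mann-Whitney, chi-square and Fisher's exact tests ignore that correlation, as does an unpaired t-test. They then hold their 5% level only by chance.

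What is at stake is the trial's only comparison, the one that serves the primary aim. Depending on the correlations, the false-positive rate could be about double the nominal level, or so far below it that real effects are missed. The text also leaves the choice between a paired and an unpaired test open, and nothing in the plan ensures that it is settled before the data are seen.

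**Working it through.** **Inputs.** From the Sample Size paragraph: n = 34, SD 15.4 (PedsQL total), difference 10 points, alpha 0.05, power 80%. Two-sided testing is assumed; the plan does not say. All between-visit correlations are assumptions. The T0–T1 interval is not fixed either, since "Patients will have the option to attend a fall or spring set of classes".

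**The plan's own figure.** The stated inputs do not give 34. A two-sample t-test needs 39 per group. A paired t-test needs 21 if 15.4 is the SD of change. A paired test gives 34 only if the SD of the within-patient contrast is about 20.2. For a plain T1–T2 comparison that means a correlation of 1 − 20.2²/(2 × 15.4²) = 0.14. The finding does not rest on this, but it shows that the sizing does not reveal which test was meant.

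**Why pairing matters.** Let D1 = T1 − T0 and D2 = T2 − T1, and let r01, r12 and r02 be the correlations between visits.

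- Var(D1) = 2·SD²·(1 − r01); Var(D2) = 2·SD²·(1 − r12)
- Cov(D1, D2) = SD²·(r01 + r12 − 1 − r02)
- Var(D2 − D1) = SD²·(6 − 4·r01 − 4·r12 + 2·r02)

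The unpaired test uses Var(D1) + Var(D2). The true variance is that sum times k = 1 − 2·Cov/(Var(D1) + Var(D2)). The true error rate is therefore roughly 2·Φ(−1.997/√k), where 1.997 is the 5% critical value of t on 66 degrees of freedom. With equal correlations, Cov = −SD²(1 − rho), so corr(D1, D2) = −0.5 and k = 1.5 whatever rho is. Then 1.997/√1.5 = 1.63, a rate of about 10%. With AR(1), corr(D1, D2) = −(1 − rho)/2.

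**Simulated error rates at nominal 5%** (40,000 trials; 10,000 for Mann-Whitney), for rho = 0.3 / 0.5 / 0.7:

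| Pattern (SD 15.4) | corr(D1, D2) | Unpaired t | Mann-Whitney |
|---|---|---|---|
| Equal correlation | −0.50 | 10.7 / 11.0 / 10.9% | 10.0 / 10.4 / 10.5% |
| AR(1), equal spacing | −0.35 / −0.25 / −0.15 | 9.0 / 7.8 / 6.9% | 8.5 / 7.7 / 6.9% |
| Short T0–T1 gap: r01 = 0.9, r02 = 0.9·rho | −0.13 / −0.11 / −0.09 | 6.1 / 6.5 / 5.8% | 7.0 / 7.1 / 6.0% |
| Short T0–T1 gap: r01 = 0.9, r02 = rho | −0.19 / −0.22 / −0.29 | 6.7 / 7.2 / 7.9% | 8.0 / 8.0 / 8.8% |

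- Individual linear trends (slope SD 5, noise SD 3, total SD 15.4 at T1): corr(D1, D2) = +0.37 and the unpaired t falls to about 1.5%. With slope SD 5 and noise SD 5 the correlation is zero and the rate is about 5%.
- Paired t: about 5% in every case.
- Raw T1 against T2 scores, unpaired t (k = 1 − rho): about 2 / 0.7 / 0.1%.
- A before/after yes/no factor at 50% prevalence (latent-normal rho, 20,000 trials): chi-square 2.5 / 1.5 / 0.5%, Fisher 1.4 / 0.8 / 0.2%, McNemar 4.0–4.4%.

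**Power for 10 points with 34 patients, paired test** (noncentral t), rho = 0.3 / 0.5 / 0.7:

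| Contrast | SD of contrast | Power |
|---|---|---|
| T2 − T1 | 18.2 / 15.4 / 11.9 | 87 / 96 / 99.7% |
| D2 − D1, equal correlation | 31.6 / 26.7 / 20.7 | 43 / 56 / 78% |
| D2 − D1, AR(1) | 29.9 / 24.3 / 18.1 | 47 / 64 / 88% |
| D2 − D1, short gap, r02 = 0.9·rho | 20.3 / 17.6 / 14.3 | 80 / 90 / 98% |
| D2 − D1, short gap, r02 = rho | 20.7 / 18.2 / 15.4 | 78 / 87 / 96% |

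**The case against.** The strongest defence is that Section V is loosely worded rather than wrong. Control group may mean the control period, the t-test may be meant as paired (the sizing supports this), and Section IV already states the within-patient contrast. The group sentence is about clinical factors, so applying it to PedsQL is an inference. Chi-square and Fisher's exact tests are valid for separate subgroups, such as the response strata in the Lay Summary. The simulated rates run from 0.1% to 11% on assumed correlations, and part of the Mann-Whitney excess in the short-gap cases comes from unequal spread: independent samples with SDs of 6.9 and 18.2 already give 6.2%.

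Some of this stands. The t-test alone is not a proven error, the size of the harm is not known, and an ambiguous text can be settled before the data are seen. The rest does not rescue the section. The named fallback is Mann-Whitney, the two-sample counterpart, not a signed-rank test. If the group sentence excludes PedsQL, the outcome used for sizing has no rule beyond the same list of tests. The categorical sentence directly follows the baseline/post comparison, and the trial collects factors that can change over time, such as the Physician Global Assessment and medication use; Section V mentions no subgroup comparison.

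**Conclusion.** The concern holds. Section V describes a two-group comparison that the design cannot supply, and three of its named tests do not suit repeated measurements on the same patients. This follows from the text alone and needs no assumption.

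The size does rest on assumptions. For the comparison in Section IV, an unpaired t-test at nominal 5% has a true rate of roughly 6–11% under the correlation patterns tried, or about 1.5% with strong individual trends. On raw before/after scores it is 0.1–2%. The 11% figure is one scenario and not the expected error. Because the error can go either way and the plan gives nothing to decide which, Section V should be corrected before any analysis.

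**What to change.** In Section V:

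- Delete the phrase about the yoga and control group. State that the contrast in Section IV, (T2 − T1) − (T1 − T0) in PedsQL total, is analysed within patient.
- Report its mean and 95% confidence interval, with a paired (one-sample) t-test as the main test. Name the Wilcoxon signed-rank test in advance as a sensitivity analysis, not as a switch after looking at the distribution.
- For categorical factors before and after yoga in the same patients, use McNemar's test, or a marginal-homogeneity test with more than two categories.
- Keep Mann-Whitney, chi-square and Fisher's exact tests for comparisons of separate subgroups only.

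Three related clarifications would help but are not needed for the correction. Confirm that PedsQL total is the primary outcome, since the aim says only HRQOL and IMPACT III is also collected. Report each patient's T0–T1 interval, because the two changes may cover unequal periods. In the Sample Size paragraph, say which contrast the 80% power refers to and give the assumed SD of that contrast in place of the control-group SD.

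The cost is wording; no data, visits or patients are added. The stated power may change: with 34 patients, the Section IV contrast reaches 80% for 10 points only if its SD is at most about 20.2.

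### Section V names only a t-test or Mann-Whitney U for a repeated, own-control design: pairing and missing questionnaires are left open, and a repeated-measures model would use the scheduled data better

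*Combined protocol and SAP*

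**What the plan says.** **Schedule.** Section IV (Participants and Enrollment) states: "Data collection surveys will be initially completed at the time of consent (time 0), start of the yoga (time 1) session", then at the end of yoga (time 2) and three months later (time 3). The Lay Summary agrees on the last visit: "They will also complete the questionnaires three months after finishing the class sessions".

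**Contrast.** Section IV makes each patient their own control and compares the time 0 to 1 change with the time 1 to 2 change. That is (T2-T1)-(T1-T0) = T2-2·T1+T0.

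**Test.** Section V (Planned Data Analysis) says: "For continuous variables whose distributions approximate normality, a t-test will be used for comparisons". If normality fails, the Mann-Whitney U test is used. The differences are described as compared between a yoga group and a control group, although the design has no separate control group.

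**Size.** The Sample Size paragraph sets 34 patients and says "there will be 80% power to detect a 10-point increase (improvement) in average total PedsQL score", using a "standard deviation of the total score in the Control group = 15.4".

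The documents give no missing-data method, analysis set, dropout allowance or within-patient correlation. They name no model that uses the time points together.

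**The concern.** The design produces up to four correlated scores per child, and the named tests use them poorly whichever way they are run.

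- **Paired.** This matches the own-control design, but a child without T0, T1 or T2 drops out of the primary contrast, even if the other scores are on file.
- **Unpaired.** This is the natural form of Mann-Whitney U, and one reading of an unspecified t-test. A child with T0 and T1 only still supplies a control-period change. But the two changes from one child share T1 and are not independent.

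T1 enters the contrast with weight -2. If children with low T1 scores are less likely to return T2, those who remain have high T1 scores. That inflates the control-period change and shrinks the yoga-period change. The protocol makes some loss plausible. The modifications to the routine allow a child with a flare to be kept out of class that day, and the five-question follow-up form goes only to those who completed at least nine classes, so incomplete attendance is foreseen.

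**Working it through.** **1. The plan's own figure.** Inputs from Sample Size: 10 points, SD 15.4, "probability of Type I error (alpha) of 0.05", "probability of Type II error (beta) of 0.20". Sidedness is not stated. By the normal approximation:

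- two-sample, two-sided: 2 × (1.960+0.842)² × 15.4²/10² = 37.2, so 38 per group;
- paired, two-sided, with 15.4 taken as the SD of change: half of that, 18.6, so 19 (21 with the t distribution).

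Neither gives 34 in total. Unstated steps can reach it, such as one-sided 30 per group inflated for 10% loss (30/0.9 = 33.3). That is a separate matter and does not decide this point. It matters here only because the plan states no allowance for missing questionnaires.

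**2. Bias formulas.** Assume SD 15.4 at each time and equal correlation ρ between times. Let s be the rise in mean T1 among children who return T2. Their mean T0 and T2 then each rise by ρs.

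- Paired, complete cases: ρs - 2s + ρs = -2(1-ρ)s.
- Unpaired, available cases: the yoga change shifts by ρs - s, and the control change, taken from everyone, does not shift. The bias is -(1-ρ)s.

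**3. Numbers.** Assumed: 20% lose T2, with probability logistic in T1, and the intercept set to give 20%. The mean T1 among those retained rises by 0.079, 0.144 and 0.231 SD for odds ratios of 1.5, 2.2 and 4.7 per SD lower T1. Multiplying by 15.4 gives s.

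| Odds per SD lower T1 | s (points) | Paired, ρ = 0.4 / 0.6 / 0.8 | Unpaired, ρ = 0.4 / 0.6 / 0.8 |
|---|---|---|---|
| 1.5 | 1.22 | -1.46 / -0.97 / -0.49 | -0.73 / -0.49 / -0.24 |
| 2.2 | 2.21 | -2.65 / -1.77 / -0.88 | -1.33 / -0.88 / -0.44 |
| 4.7 | 3.55 | -4.26 / -2.84 / -1.42 | -2.13 / -1.42 / -0.71 |

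Simulation with n = 34 (6,000 trials per scenario) agrees: about -0.5 to -4.2 paired and -0.2 to -2.1 unpaired. The likelihood estimate regresses T2 on T0 and T1 in those with T2, then averages over everyone. Its bias is within about 0.1 point throughout.

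**4. Precision, 20% lost at random.** SD of the estimate over simulated trials:

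| ρ | Paired complete | Unpaired available | Likelihood |
|---|---|---|---|
| 0.5 | 5.14 | 4.81 | 4.78 |
| 0.6 | 4.58 | 4.23 | 4.19 |
| 0.7 | 3.93 | 3.63 | 3.59 |

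Against complete cases the variance falls by 1-(4.78/5.14)² = 14% at ρ = 0.5 and about 16% at ρ = 0.6. Against available cases it falls by 1-(4.78/4.81)² = 1% to 1-(3.59/3.63)² = 2%.

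**5. Unpaired standard error, no data missing.** Each change has variance 2(1-ρ)σ², and the covariance of the two is -(1-ρ)σ². The true variance of the contrast is 6(1-ρ)σ²/n. An unpaired test uses 4(1-ρ)σ²/n, so its standard error is too small by a factor √(4/6) = 0.82.

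**6. Loss driven by the unseen T2 score.** With 20% loss and log-odds 1 per SD lower T2, the likelihood estimate is biased by +1.8 (ρ = 0.5) and +1.3 (ρ = 0.7). Complete cases are biased by +1.3 and +0.9.

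**The case against.** A reader might infer that the named tests can use only children with T0, T1 and T2, so that one missing questionnaire always loses the child. The documents do not support that. The t-test is not said to be paired, and Mann-Whitney U is an independent-samples test. Run unpaired, a child with T0 and T1, or with T1 and T2, still contributes one change; only a missing T1 removes both. A child missing only T3 keeps the full contrast under either reading. This stands, and it halves the bias for the unpaired reading. It does not clear the plan: that reading is still biased and uses a standard error that is too small.

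The size also rests on assumptions. The documents give no loss rate, no correlation and no link between loss and T1. Section IV requires gastroenterologist clearance in the 8 weeks before yoga, which may remove some of the least well children before T1. Nothing in the protocol shows that children less well at the first class are the likeliest to stop. With a weak link (1.5-fold), the paired bias is at most about 1.5 points. This stands as a limit on confidence.

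The bias from T1-dependent loss is towards no effect, so it does not by itself create a false claim of benefit. That is right for the estimate. Under the unpaired reading, though, the understated standard error works the other way.

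Finally, the calculations cover three times with loss at T2 only. A four-time model with intermittent gaps in about 34 children was not simulated.

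**Conclusion.** The concern holds in a limited form. Section V fixes neither the form of the test nor the handling of missing questionnaires. If T2 loss depends on T1, either reading understates the yoga effect: by about 0.5 to 4.2 points paired or 0.2 to 2.1 unpaired, against a 10-point target. This assumes 20% loss, correlation 0.4 to 0.8, and 1.5- to 4.7-fold odds of loss per SD lower T1.

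Two stronger conclusions should not be drawn. A mixed model is not a complete cure: it removes bias only when loss depends on observed scores and the model is adequate. When loss followed the unseen T2 score, it was more biased than complete cases, and in the direction of benefit. Nor is precision the main argument: the variance gain is about 14-16% over complete cases but only 1-2% over available cases. The case rests on bias under plausible loss, correct treatment of within-child correlation, and prespecification. The change should be made, with medium confidence in its practical size.

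**What to change.** In Section V, make the primary analysis of PedsQL, and the analyses of IMPACT-III and self-efficacy, a repeated-measures mixed model with:

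- time (0, 1, 2, 3) as a category;
- an unstructured within-patient covariance, with a named simpler structure if it does not converge;
- a small-sample degrees-of-freedom correction;
- all enrolled patients with any questionnaire.

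Estimate (T2-T1)-(T1-T0) as a model contrast with a 95% CI, and state the missing-at-random assumption. Keep the complete-case t-test, stated to be paired, as a sensitivity analysis. Add a second sensitivity analysis for loss that depends on the unseen T2 score, for example by shifting imputed T2 values over a stated range. Remove the reference to a separate control group.

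**Cost.** New wording and slightly more analysis work; no extra patients or questionnaires. Section V commits all analyses to MINITAB 17, so the sponsor should confirm that it can fit this model or name other software. Bias from loss driven by unrecorded events after T1 would remain, so reasons for missing questionnaires are worth recording.
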